7.9.2 Secondary Objectives

7.9.2.1 Secondary Objective 1: Overall Response Rates

This objective is to characterize the efficacy of spinal cord stimulation (SCS) therapy for the treatment of overall pain (for low-back and/or leg pain subjects) by evaluating the efficacy responder rate. The efficacy responder rate is defined as the percentage of implanted subjects who experience at least a 50% improvement in overall pain, as measured by the Visual Analogue Scale (VAS), from Baseline to the 3-Month Visit.

7.9.2.1.1 Hypothesis

There is no hypothesis test for this objective. The purpose is to characterize the overall efficacy responder rate at the 3-Month Visit.

7.9.2.1.2 Endpoint definition and derivation

A responder will be any low-back and/or leg pain subject who demonstrates at least a 50% improvement (percent change) in overall pain as measured by the VAS, calculated as follows:

- Absolute change (Δ) at the subject level will be calculated as:

$$\Delta = \text{VAS}_{\text{Follow-up}} - \text{VAS}_{\text{Base}}$$

Where VAS_{Base} and $\text{VAS}_{\text{Follow-up}}$ are the value of the overall VAS pain score at baseline and follow up, respectively. A negative value indicates an improvement (reduction) in pain.

- Percentage change at the subject level will be calculated as 100 times the absolute change divided by the baseline value.

$$\text{Percentage change} = 100 * \Delta / \text{VAS}_{\text{Base}}$$

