10.4 Prior and Concomitant Medications

Only prescribed medications used for the treatment of low-back, leg pain and upper limb pain will be collected during the study.

Any changes to subject's pain medications while they are enrolled in the study will be documented in the subject's medical records and the study database.

All medications used to treat adverse events (regardless of their reason prescribed) will be documented on an eCRF.

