10.20 System Modification

System modifications (e.g. lead or device revision, replacement, or explant) may occur in the study due to ineffective or loss of therapy, AEs, device deficiencies, or subject concerns that are not correctable by programming. In the event of a system modification, the visit schedule for the subject will remain unchanged. If the SCS device requires replacement, contact a member of the Medtronic study team as the decision to allow re-implant will be handled on a case-by-case basis. If the system is explanted, the explanted system will be returned to Medtronic. All explanted products should be returned to Medtronic for analysis when permissible by local laws and regulations. See Sections 7.10 and 7.11 for final product disposition details.

The following information is required to be collected during system modification visits:

- Changes to the implanted system
- Collect data files via the clinician programmer tablet and securely send to Medtronic
- Fluoroscopy/x-ray, if necessary
- Pain medications
- AEs/device deficiencies

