14.7 Safety Assessment

To characterize all device-related, therapy-related, and procedure-related adverse events and device deficiencies from the start of the device trial until study exit. Adverse events and device deficiencies will be summarized using summary tables displaying the frequency and percentages of events as well as the number of subjects experiencing events, by study phase, and in total. Adverse events will be summarized by seriousness as well.

[REDACTED]

[REDACTED]

[REDACTED]

[REDACTED]

[REDACTED]	[REDACTED]	[REDACTED]	[REDACTED]	[REDACTED]
[REDACTED]	[REDACTED]	[REDACTED]	[REDACTED]	[REDACTED]
[REDACTED]	[REDACTED]	[REDACTED]	[REDACTED]	[REDACTED]
[REDACTED]	[REDACTED]	[REDACTED]	[REDACTED]	[REDACTED]
[REDACTED]	[REDACTED]	[REDACTED]	[REDACTED]	[REDACTED]
[REDACTED]	[REDACTED]	[REDACTED]	[REDACTED]	[REDACTED]
[REDACTED]	[REDACTED]	[REDACTED]	[REDACTED]	[REDACTED]
[REDACTED]	[REDACTED]	[REDACTED]	[REDACTED]	[REDACTED]
[REDACTED]	[REDACTED]	[REDACTED]	[REDACTED]	[REDACTED]
[REDACTED]	[REDACTED]	[REDACTED]	[REDACTED]	[REDACTED]

For the primary objective, a subset (28) of the total device implanted low-back and/or leg pain subjects are needed to evaluate the endpoint. For the secondary objectives, up to 45 implanted subjects with low-back and/or leg pain are desired to characterize the responder rates at the 3-Month Visit. Up to 9 implanted subjects with upper limb and/or neck pain are desired to characterize the population at the 3-Month Visit.

[REDACTED]

[REDACTED]

[REDACTED]

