7.1.3 Analysis Sets

- The **All Consented Set** (ACS) will include all subjects who signed the study specific ICF and enrolled in the study.
- The **Full Analysis Set** (FAS) will include all device-implanted subjects.
- The **Primary Analysis Set** (PAS) will follow the intent-to-treat (ITT) principle to include randomized low-back and leg pain subjects who will be used for the primary objective, i.e., the first 28 randomized low-back and leg pain subjects.
- The **Complete Case Set** (CCS) will include all device-implanted subjects who have data available at baseline and follow-up. This set is defined for each outcome measure at each follow-up visit. [REDACTED]

[REDACTED]

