7.9.2.1.3 Analysis Methods

A point estimate of the proportion of responders, along with a 95% confidence interval, will be presented for this objective.

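### The 3-month responder rules rest on VAS change alone, so in the visible text explant and analgesic changes before that visit do not affect who counts as an SCS responder

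*SAP*

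**What the plan says.** Secondary objective 1 is worded in terms of the therapy: "This objective is to characterize the efficacy of spinal cord stimulation (SCS) therapy for the treatment of overall pain" (SAP 7.9.2.1). The endpoint is a threshold on the percent change in overall VAS from baseline to 3 months: "A responder will be any low-back and/or leg pain subject who demonstrates at least a 50% improvement (percent change) in overall pain" (SAP 7.9.2.1.2, and identically Protocol 14.5.1.2). Protocol 14.5.2.2 repeats the rule for back and leg VAS; the matching SAP section is not visible.

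The objective is descriptive: "There is no hypothesis test for this objective" (SAP 7.9.2.1.1). Its output is one proportion with an interval: "A point estimate of the proportion of responders, along with a 95% confidence interval, will be presented for this objective" (SAP 7.9.2.1.3). The sample-size paragraph after Protocol 14.7 says "up to 45 implanted subjects with low-back and/or leg pain are desired to characterize the responder rates at the 3-Month Visit".

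Four provisions bear on explant and analgesics:
- **System modification.** Protocol 10.20 includes explant, with failed or lost therapy among the reasons, and adds: "In the event of a system modification, the visit schedule for the subject will remain unchanged".
- **Analysis set.** SAP 7.9.2.1.4 uses the low-back and/or leg pain subjects of the CCS, which "will include all device-implanted subjects who have data available at baseline and follow-up" (SAP 7.1.3).
- **Medication.** Inclusion criterion 5 requires stable prescribed analgesics for 28 days before the device trial. After that, "Any changes to subject's pain medications while they are enrolled in the study will be documented" (Protocol 10.4). Only prescribed pain medication is collected.
- **Missing data.** The visible sensitivity analysis imputes missing 3-month VAS scores if more than 5% are missing. It does not touch an observed VAS.

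**The concern.** The objective names the efficacy of SCS therapy, but the visible rule would give the same answer for a subject with a working system, one whose system has been removed, and one whose analgesics were changed after the device trial. Both events are foreseen by the protocol and both are captured in the data, yet in the visible text neither has a consequence for the endpoint.

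The estimate and its interval are the whole result of this objective. What counts as a response should therefore be settled before the rate is read. Otherwise a reader cannot tell whether the rate means relief with the system in place, or relief by any route among subjects once implanted who supplied a VAS.

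**Working it through.** **1. What the rule needs.** Percentage change = 100 × (follow-up − baseline) / baseline, and a responder has a fall of at least 50%. At the entry threshold of 60 mm, a 3-month score of 30 mm gives 100 × (30 − 60) / 60 = −50%, a responder. Device status and medication are not terms in this formula.

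**2. Explant, followed through the plan.**
- By the windows in Protocol Table 6, the 3-month VAS falls between 9 + 75 = 84 and 16 + 105 = 121 days after implant, so explant can precede it.
- The visit schedule then continues (Protocol 10.20). Explant of an implanted system is not a named exit reason in Protocol 10.25.1, although withdrawal by the subject or investigator could follow. SAP 7.10 ends device exposure at explant or at study exit, if later, which is consistent with follow-up beyond explant.
- If a 3-month VAS is obtained, the subject was implanted and has both scores, so is in the CCS and is classified on VAS alone.
- If none is obtained, the subject leaves the CCS and the denominator, although a removed system is relevant to the efficacy of the therapy.
- SAP 7.4 names the Full Analysis Set (FAS) for the secondary objectives instead. The FAS holds all implanted subjects, so explanted subjects stay in it too.

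**3. Medication, followed through the plan.** The longest span from device trial to the end of the 3-month window is 10 + 60 + 16 + 105 = 191 days, of which 10 + 60 + 16 = 86 precede device activation. This is the sum of every window maximum, so it is an upper limit. Changes in that span are recorded at visits and phone calls, but do not enter the rate.

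**4. Direction.**
- Explanted subject with a low VAS: counted as a responder, raises the rate.
- Added analgesic: may lower the VAS, tends to raise the rate.
- Reduced analgesic: may raise the VAS, tends to lower the rate. Protocol 4.1 cites medication reduction among the outcomes reported with SCS, so this case is realistic.

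The net effect cannot be signed from the documents.

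**5. Size.** The visible text gives no expected responder rate or precision target for this objective, only the count of up to 45, so there is no planned figure to reproduce. Each reclassified responder moves the rate by 1/45 = 2.2 points. The starting rates and event counts below are assumptions; intervals are exact (Clopper-Pearson), also assumed, as no method is visible.

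| Reclassified | Start 36/45 | Start 27/45 |
|---|---|---|
| 0 | 80.0% (65.4 to 90.4) | 60.0% (44.3 to 74.3) |
| 1 | 77.8% (62.9 to 88.8) | 57.8% (42.2 to 72.3) |
| 2 | 75.6% (60.5 to 87.1) | 55.6% (40.0 to 70.4) |
| 3 | 73.3% (58.1 to 85.4) | 53.3% (37.9 to 68.3) |
| 5 | 68.9% (53.4 to 81.8) | 48.9% (33.7 to 64.2) |

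An explanted subject without a 3-month VAS acts through the denominator: adding one as a non-responder to 36/45 gives 36/46 = 78.3%, a fall of 1.7 points.

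**The case against.** **A descriptive rate in a feasibility study does not need this.** It is true that there is no hypothesis, so no error rate or success decision is affected. What stands against the objection is that the rate is the only product of the objective, and its meaning depends on the classification.

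**Counting VAS regardless of medication is a recognised treatment-policy choice.** This stands, and it is why medication should not alter the main rate. It is less persuasive for explant, where the therapy named in the objective is no longer present.

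**The explant route is narrow.** A subject explanted within about three months who still attends and reports at least 50% relief is probably uncommon, and an explanted subject with no 3-month VAS may be the more likely case. Both are fair points. The fix covers both cases.

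**A reader might infer that the rate is biased in favour of the device.** The documents do not support that, because the visible rule ignores analgesic reductions as well as increases.

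**A reader might infer that the plan contains no handling at all.** That cannot be said either. Text is redacted in Protocol 14.5.1, after the CCS definition in SAP 7.1.3, and after SAP 7.9.2.1.4. The point is limited to the visible text, but the overall-pain endpoint definitions and analysis method are themselves legible.

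**Conclusion.** The point holds as a gap in the visible definition. Applied as written, the plan can count a subject with no system in place as a responder to SCS, can lose an explanted subject without a 3-month VAS from the CCS, and makes no use of medication changes that it records.

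The size is 2.2 points per reclassified subject at n = 45. Two such subjects would move an assumed 80.0% to 75.6%, which is still inside the starting interval of 65.4 to 90.4. How many subjects are affected is unknown, as no event rate is given, and the net direction of the medication effect is unknown.

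A reader might also infer that a handling rule would make the rate a measure of the SCS effect. It would not: there is no concurrent control for this rate, subjects enter on a VAS of at least 60 mm, and expectation and regression to the mean remain under any rule. The gain is a rate whose meaning is stated, with no change to any test.

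**What to change.** In SAP 7.9.2, for the overall and the pain-specific rates:

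1. Classify a low-back and/or leg pain subject whose system was explanted without re-implant before the 3-month VAS as a non-responder, whether or not a later VAS exists, and keep that subject in the denominator. State that this overrides the CCS data requirement and any imputation, and settle whether the CCS (SAP 7.9.2.1.4) or the FAS (SAP 7.4) is the base set. For the pain-specific rates, apply the rule within the subjects meeting the 60 mm baseline threshold.
2. Keep the VAS-only rate as the main rate with respect to medication, and say that this is intended. Beside it, report a supportive rate in which a net increase or new start of prescribed pain medication since baseline counts as non-response. Because that rate can only be equal or lower, add a table of medication increases and decreases by responder status so that both directions are visible.

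The cost is SAP wording, one supportive rate and one table, from data already collected. Item 1 changes the derivation of a secondary endpoint, so the difference from Protocol 14.5 should be noted in the study report, as Protocol section 14 requires for deviations. If Protocol 14.5 is amended as well, Protocol 16.6 requires ethics committee approval before sites implement it.

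Downsides: a definition of net increase is needed, non-prescribed analgesics are not recorded and cannot be counted, and the reported rates may be slightly lower.

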7.9.2.1.3 Analysis Methods

A point estimate of the proportion of responders, along with a 95% confidence interval, will be presented for this objective.

7.9.2.1.4 Determination of Subjects/Data for Analysis

Information from low-back and/or leg pain subjects who provide data at baseline and the 3-Month Visit (low-back and/or leg pain subjects from the CCS) will be used for this objective.

As a sensitivity analysis, if there is greater than 5% of subjects with missing values, any subjects who were device-implanted (FAS) but are missing their VAS scores at the 3-Month Visit will be imputed using Multiple Imputation (MI). Prior to the use of MI, the distributions of the continuous variables will be assessed for normality and transformation may be considered if they are not normally distributed.

[REDACTED]

Following imputation, the objective will be evaluated using MI analysis method.

[REDACTED]

[REDACTED]

[REDACTED]

[REDACTED]	[REDACTED]	[REDACTED]	[REDACTED]	[REDACTED]	[REDACTED]	[REDACTED]	[REDACTED]
[REDACTED]	[REDACTED]	[REDACTED]	[REDACTED]	[REDACTED]	[REDACTED]	[REDACTED]	[REDACTED]
[REDACTED]	[REDACTED]	[REDACTED]	[REDACTED]	[REDACTED]	[REDACTED]	[REDACTED]	[REDACTED]
[REDACTED]	[REDACTED]	[REDACTED]	[REDACTED]	[REDACTED]	[REDACTED]	[REDACTED]	[REDACTED]
[REDACTED]	[REDACTED]	[REDACTED]	[REDACTED]	[REDACTED]	[REDACTED]	[REDACTED]	[REDACTED]
[REDACTED]	[REDACTED]	[REDACTED]	[REDACTED]	[REDACTED]	[REDACTED]	[REDACTED]	[REDACTED]
[REDACTED]	[REDACTED]	[REDACTED]	[REDACTED]	[REDACTED]	[REDACTED]	[REDACTED]	[REDACTED]
[REDACTED]	[REDACTED]	[REDACTED]	[REDACTED]	[REDACTED]	[REDACTED]	[REDACTED]	[REDACTED]
[REDACTED]	[REDACTED]	[REDACTED]	[REDACTED]	[REDACTED]	[REDACTED]	[REDACTED]	[REDACTED]
[REDACTED]	[REDACTED]	[REDACTED]	[REDACTED]	[REDACTED]	[REDACTED]	[REDACTED]	[REDACTED]
[REDACTED]	[REDACTED]	[REDACTED]	[REDACTED]	[REDACTED]	[REDACTED]	[REDACTED]	[REDACTED]
[REDACTED]	[REDACTED]	[REDACTED]	[REDACTED]	[REDACTED]	[REDACTED]	[REDACTED]	[REDACTED]
[REDACTED]	[REDACTED]	[REDACTED]	[REDACTED]	[REDACTED]	[REDACTED]	[REDACTED]	[REDACTED]
[REDACTED]	[REDACTED]	[REDACTED]	[REDACTED]	[REDACTED]	[REDACTED]	[REDACTED]	[REDACTED]
[REDACTED]	[REDACTED]	[REDACTED]	[REDACTED]	[REDACTED]	[REDACTED]	[REDACTED]	[REDACTED]
[REDACTED]	[REDACTED]	[REDACTED]	[REDACTED]	[REDACTED]	[REDACTED]	[REDACTED]	[REDACTED]
[REDACTED]	[REDACTED]	[REDACTED]	[REDACTED]	[REDACTED]	[REDACTED]	[REDACTED]	[REDACTED]

[Redacted]

[Redacted]

[Redacted]

[Redacted]

[Redacted]

[Redacted]

[Redacted]

[Redacted]

[Redacted]

[Redacted]

[Redacted text block]

[Redacted text block]

[Redacted text block]

[Redacted text block]

[Redacted text block]

[Redacted text block]

[Redacted text block]

- [Redacted list item]
- [Redacted list item]
- [Redacted list item]
- [Redacted list item]

[Redacted text block]

[Redacted text block]

[Redacted text block]

[Redacted text block]

[Redacted text block]

[Redacted text block]

[Redacted text block]

[Redacted text block]

- [Redacted list item]
- [Redacted list item]
- [Redacted list item]
- [Redacted list item]
- [Redacted list item]

[Redacted text block]

[Redacted text block]

[Redacted text block]

[figure not shown]
[Redacted]

[Redacted]

[Redacted]

- [Redacted]
- [Redacted]
- [Redacted]
- [Redacted]
- [Redacted]

[Redacted]

[Redacted text block]

[Redacted text block]

[Redacted text block]

[Redacted text block]

[Redacted text block]

[Redacted text block]

[Redacted text block]

[Redacted text block]

[Redacted text block]

[Redacted text block]

[Redacted text block]

[Redacted text block]

[Redacted text block]

[Redacted text block]

[Redacted text block]

- [Redacted list item]
- [Redacted list item]
- [Redacted list item]
- [Redacted list item]
- [Redacted list item]
- [Redacted list item]
- [Redacted list item]

[Redacted text block]

[Redacted text block]

[REDACTED]

[REDACTED]

[REDACTED]

[REDACTED]

[REDACTED]

- [REDACTED]
- [REDACTED]
- [REDACTED]
- [REDACTED]

[REDACTED]

[REDACTED]

[REDACTED]

[REDACTED]

[REDACTED]

[REDACTED]

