Secondary Objectives	
1. To characterize the efficacy of spinal cord stimulation (SCS) therapy for the treatment of overall pain in low-back and/or leg pain subjects by evaluating the efficacy responder rate. The efficacy responder rate is defined as the percentage of low-back and/or leg pain implanted subjects who experience at least a 50% improvement in overall pain, as measured by the Visual Analogue Scale (VAS), from Baseline to the 3-Month Visit.2. To characterize the efficacy responder rate of low-back pain and leg pain in low-back and/or leg pain subjects, as measured by the pain-specific VAS, from Baseline to the 3-Month Visit. The low-back responder rate will be characterized for subjects with baseline back VAS \geq 60 mm, and the leg responder rate will be characterized for subjects with baseline leg VAS \geq 60 mm.
[REDACTED]	[REDACTED]

[REDACTED]

[REDACTED]

Evaluation of Long-term Patient Experience with a Medtronic Closed-Loop SCS System (Closed-Loop SCS study)

Clinical Investigation Plan

06JAN2023

Version 4.0

Page 13 of 117

Medtronic

	
[REDACTED]

Study Design	
Prospective, multi-center, randomized, single-blind, investigational, feasibility study. Eligible patients will be consented and enrolled, undergo a psychological evaluation, have an x-ray or MRI, as needed, be evaluated for baseline assessments, undergo an SCS trial and if successful, undergo the implant of a permanent INS. Following implant, subjects will have their SCS device settings optimized for the Neuro Sense feature. Following device optimization, subjects will be randomized to a sequence of Neuro Sense On and Neuro Sense Off for in-clinic testing. Subjects will then continue being followed periodically for a total study duration of up to 24-months.

Randomization	
1:1 randomization (one of the two sequences): Neuro Sense On followed by Neuro Sense Off or Neuro Sense Off followed by Neuro Sense On

[REDACTED]
	
[REDACTED]

[REDACTED]

[REDACTED]

Evaluation of Long-term Patient Experience with a Medtronic Closed-Loop SCS System (Closed-Loop SCS study)

Clinical Investigation Plan

06JAN2023

Version 4.0

Page 14 of 117

Medtronic

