4.2 Purpose

The purpose of the Closed-Loop SCS study is to further our understanding of closed-loop SCS in patients implanted with the Inceptiv INS. The Closed-loop SCS study is a prospective, multi-center, randomized,

[REDACTED]

[REDACTED]

[REDACTED]

6. Study Design

The study is expected to be conducted at up to ten study sites located in Australia. Up to 140 subjects will be enrolled in the study to ensure up to 57 subjects with low-back and/or leg pain and up to 12 subjects with upper limb and/or neck pain are implanted with the study device.

Up to 110 Inceptiv devices may be used in the study. To reduce the possibility of atypical results from a site overly influencing the study, no more than 20% of the total implanted population will be from each site unless the site gets pre-approval from Medtronic for additional implants.

Subjects will be enrolled, and baseline data will be collected. Those meeting all inclusion criteria and no exclusion criteria will undergo a device trial. Subjects with sufficient pain relief during the trial will be implanted with the study device and undergo Device Optimization for 1-Month. Approximately 1-Month post Device Activation, subjects will undergo in-clinic testing. Subjects will be randomized at the in-clinic visit to one of the two sequences: Neuro Sense On followed by Neuro Sense Off or Neuro Sense Off followed by Neuro Sense On. Subjects will be blinded to the settings tested. In each setting, subjects will perform a series of activities and asked to rate the intensity of the overstimulation sensation they experienced while performing the activity using a 5-point Likert scale. [REDACTED]

[REDACTED] It is recommended that the Neuro Sense feature be turned ON at the end of the in-clinic testing visit, unless the patient prefers the Neuro Sense OFF setting. All subjects will then be followed for up to 24-months following device activation; scheduled study visits will occur at 3-, 6-, 12-, 18-, and 24-months post device activation.

[REDACTED]

[REDACTED]

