14.5.1.4 Determination of Subjects/Data for Analysis

Information from low-back and/or leg pain subjects who provide data at baseline and the 3-Month Visit (low-back and/or leg pain subjects from the CCS) will be used for this objective.

As a sensitivity analysis, if there is greater than 5% of subjects with missing values, any subjects who were device-implanted (FAS) but are missing their VAS scores at the 3-Month Visit will be imputed using Multiple Imputation (MI). Prior to the use of MI, the distributions of the continuous variables will be assessed for normality and transformation may be considered if they are not normally distributed.

Following imputation, the objective will be evaluated using MI analysis method.

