7.4 Handling of Missing, Unused, and Spurious Data and Dropouts

Missing data are a potential source of bias when analyzing study data. A rigorous study design and execution will help prevent the incidence of missing data from occurring as described in Section 14.9. The analysis of the primary objective will use the first 28 subjects that complete in clinic testing and provide a primary endpoint (PAS) and if, across all subjects, more than 5% (Buhi, Goodson, & Neilands, 2008) of the average intensity scores for either the open loop (OL) or closed loop (CL) period are missing Multiple Imputation (MI) methodology for missing data will be utilized.

Prior to the use of MI, the distributions of the continuous average stimulation intensity variables will be assessed for normality (using the Shapiro-Wilk test) to determine if transformation of non-normal variables ($p \leq 0.05$) may be considered, or if a different imputation specification that is more appropriate for non-normal data may be used.

[REDACTED]
[REDACTED]
[REDACTED]
[REDACTED] Following imputation, the objective will be evaluated using MI analysis methods.

The FAS will be used for the analysis of all secondary objectives and if more than 5% of subjects have missing VAS scores at baseline or the 3-month visit then MI methodology for missing data will be utilized.

[REDACTED]
[REDACTED]
[REDACTED]
[REDACTED]

[REDACTED] [REDACTED] [REDACTED]

[REDACTED] Following imputation, the objective will be evaluated using MI analysis methods.

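### Secondary Objective 1 is defined over all implanted subjects, but its main estimate divides only by those with 3-month data

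*SAP*

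**What the plan says.** **Definition.** In the Protocol synopsis the rate is "defined as the percentage of low-back and/or leg pain implanted subjects who experience at least a 50% improvement in overall pain". SAP 7.9.2.1 says that the "efficacy responder rate is defined as the percentage of implanted subjects who experience at least a 50% improvement in overall pain", and Protocol 14.5.1 agrees. The stated denominator is therefore implanted subjects.

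**Main analysis set.** SAP 7.9.2.1.4 uses "Information from low-back and/or leg pain subjects who provide data at baseline and the 3-Month Visit (low-back and/or leg pain subjects from the CCS"). Protocol 14.5.1.4 has the same rule ("low-back and/or leg pain subjects from the CCS) will be used for this objective"), and the statistics part of the synopsis also restricts these objectives to subjects with both measurements. SAP 7.1.3 defines the complete case set (CCS) as one that "will include all device-implanted subjects who have data available at baseline and follow-up".

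**Imputation.** In Protocol 14.5.1.4 and SAP 7.9.2.1.4, multiple imputation (MI) in the full analysis set (FAS, all implanted subjects) is a sensitivity analysis, run only if more than 5% are missing. SAP 7.4 reads differently: "The FAS will be used for the analysis of all secondary objectives and if more than 5% of subjects have missing VAS scores", MI is applied.

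**Counts.** Protocol section 6 plans that "up to 57 subjects with low-back and/or leg pain and up to 12 subjects with upper limb and/or neck pain are implanted". SAP section 5 still has up to 50 low-back/leg implants. The sample-size text after Protocol 14.7 says that "up to 45 implanted subjects with low-back and/or leg pain are desired to characterize the responder rates at the 3-Month Visit", and SAP section 6 gives the same 45. The Protocol version history raises the implant number from 50 to 57 because of concern about attrition.

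**The concern.** An implanted subject with no 3-month VAS belongs to the stated denominator but leaves the one that is used. If such subjects do worse than those who return, the completer percentage overstates the share of implanted subjects who obtained relief. Secondary Objective 1 has no hypothesis test (Protocol 14.5.1.1, SAP 7.9.2.1.1), so the point estimate and its interval are the whole result. A completer percentage reported under a definition that says implanted would be misread. The version history shows that the sponsor already expected missing data to be a practical problem.

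**Working it through.** The readable text gives no responder rate or gap for this objective, so there is no planned figure to reproduce. The attrition rate is not readable either. As a consistency check, 45/(1 − 0.20) = 56.25, which rounds up to 57, and 45/(1 − 0.10) = 50. The two implant counts therefore fit about 20% and 10% attrition.

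**Inputs**
- N = implanted low-back/leg subjects: 57 (Protocol section 6) or 50 (SAP section 5).
- Subjects with 3-month data: 45 (both documents).
- m = N − 45 = 12 or 5 missing, that is 12/57 = 21.1% or 5/50 = 10.0%.
- p = responder rate among completers. Assumed 80%. The plan sets no value; rates of about this size appear only as background from other studies (Protocol 4.1).
- q = responder rate among missing subjects. Unknown, so varied from 0 to 1.

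**Formula**

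All-implanted rate = (45p + mq)/N. Gap = p − (45p + mq)/N = (p − q) × m/N.

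**Every missing subject a non-responder (q = 0), p = 80%, so 36 responders.** The 95% intervals are exact binomial, which is my assumption about the method.
- CCS: 36/45 = 80.0% (65.4% to 90.4%).
- Protocol counts: 36/57 = 63.2% (49.3% to 75.6%), gap 16.8 points.
- SAP counts: 36/50 = 72.0% (57.5% to 83.8%), gap 8.0 points.

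**Gap in points at p = 80% as q varies**

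| q | N = 57 | N = 50 |
|---|---|---|
| 0 | 16.8 | 8.0 |
| 25% | 11.6 | 5.5 |
| 50% | 6.3 | 3.0 |
| 80% | 0 | 0 |
| 100% | −4.2 | −2.0 |

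**Gap in points at q = 0 as p varies**

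| p | N = 57 | N = 50 |
|---|---|---|
| 50% | 10.5 | 5.0 |
| 60% | 12.6 | 6.0 |
| 70% | 14.7 | 7.0 |
| 90% | 18.9 | 9.0 |

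**Below the MI trigger.** With N = 57, 5% is 2.85 subjects, so at most 2 can be missing without triggering MI. The gap is then at most 0.80 × 2/57 = 2.8 points. With 12 of 57 or 5 of 50 missing, the trigger is met and an FAS estimate would be produced.

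**How conservative the q = 0 figure is.** With N = 57 and q = 50%, the all-implanted rate is (36 + 6)/57 = 73.7%. The CCS rate is 6.3 points too high and the q = 0 rate 10.5 points too low. The two errors are equal when p − q = q, that is at q = 40%. The q = 0 rate is therefore a bound and not an unbiased estimate.

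**The case against.** Four points on the other side carry weight.

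- **MI on the FAS keeps every implanted subject in the denominator.** It is planned in both places, and at 10% or 21% missing it would run. A reader might infer that no planned analysis targets implanted subjects, and the documents do not support that. What remains is that SAP 7.9.2.1.4 gives MI only sensitivity status, and that no readable analysis counts observed responders over all implanted subjects.
- **The definition does not say that a missing score is a failure.** It refers to subjects who experience improvement. Counting missing subjects as non-responders is the analyst's choice, and it errs low if some of them did benefit. This stands and governs how the extra figure must be labelled.
- **MI may perform well.** No VAS is scheduled between baseline and month 3, so one might infer that imputed values would mostly copy the completers. But Protocol 10.17 requires a 0–10 pain score at weekly calls over that period, and the imputation model is redacted, so this cannot be judged.
- **Explanted subjects are not removed by rule.** A reader might infer that those whose system is taken out for lack of effect are the ones lost. Protocol 10.20 leaves the visit schedule unchanged after a system modification, including explant, and explant after implantation is not a listed exit reason in 10.25.1. Voluntary withdrawal is listed, so missingness related to outcome is possible, but neither document states that it occurs.

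The synopsis also discloses that available data are used, and attrition will be summarised (Protocol 14.1.4, SAP 7.1.1). That lessens the problem, but it does not make the definition and the main denominator agree.

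**Conclusion.** The mismatch holds in both documents: the rate is defined over implanted low-back/leg subjects and its main estimate is computed over those with 3-month data. SAP 7.4 and 7.9.2.1.4 also disagree on whether the FAS or the CCS is the analysis set.

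The effect is at most 16.8 points (45 of 57) or 8.0 points (45 of 50) at an assumed 80% completer rate with all missing subjects counted as non-responders. It falls to zero if missing subjects respond at the completers' rate and reverses if they respond better. It would be tempting to say that the plan's own numbers imply an overstatement of about 17 points. They do not: that figure needs the larger implant count, a completer rate that the plan never sets, and universal failure among the missing. The numbers 57, 50 and 45 are also all ceilings or targets, not expected counts.

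No test decision is affected. The matter is worth correcting because the estimate is the result for this objective and its label would be wrong.

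**What to change.** In SAP 7.9.2.1.4 and Protocol 14.5.1.4:

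1. Label the CCS rate as being among subjects with 3-month data.
2. Beside it, report observed responders divided by all implanted low-back/leg subjects, with a 95% CI, described as a conservative lower bound and not as the defined rate itself.
3. Keep the MI estimate in the FAS as the model-based figure for all implanted subjects. Amend SAP 7.4 or 7.9.2.1.4 so that both name the same main analysis set.
4. List the number of implanted subjects without a 3-month VAS and the reasons.

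Add the same row for Secondary Objective 2 (Protocol 14.5.2.4 and the matching SAP text), among implanted subjects with baseline back or leg VAS of at least 60 mm. That definition does not itself say implanted, so there the row adds information and does not repair a contradiction.

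The cost is a wording change, one table row per rate and a short listing. The downside for the sponsor is one additional, less favourable figure beside each rate.
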